2.2 SUBJECTS

Up to 70 total study subjects will be recruited from the five FEP clinics in North Carolina (OASIS, Encompass, Eagle, SHORE, and AEGIS) and their stepdown outpatient clinics (STEP and TIDES), including up to 50 FEP clients and 20 FEP providers (clinicians and PSS). All subjects will have a primary diagnosis of schizophrenia spectrum disorder. Demographic and clinical information that will be collected as self-report for possible use as covariates includes: 1) demographics: age, sex & gender identity, race & ethnicity, education, parent education; 2) health: smoking, substance use, current medications, and DUP.

2.2.1 INCLUSION CRITERIA

1. Clients must be between the ages of 16 and 35
2. Clients must have a primary diagnosis of schizophrenia, schizoaffective disorder, schizopreniform disorder, or Unspecified Schizophrenia Spectrum or Other Psychotic disorder
3. Clients must be receiving services at one of the five FEP clinics in North Carolina (OASIS, Encompass, Eagle, SHORE, AEGIS) or FEP clinics stepdown care clinics (STEP and TIDES)
4. Clients must not have had thoughts of harming themselves in the month before enrollment
5. Clients must not have been hospitalized for psychiatric reasons in the three months before enrollment
6. Clients must have been actively engaging in psychiatric medication management in the prior month
7. Clients must have access to the internet through a phone, tablet, or computer

2.2.2 EXCLUSION CRITERIA

1. Clients who do not speak English will not be considered for enrollment
2. Clients with legal guardians (LARs) will not be considered for the study

3 ASSESSMENT OF DATA

At this stage of treatment development, specific outcomes include:

1. Identifying barriers and facilitators of implementing Horyzons at NC FEP clinics through the following:
 - Conducting qualitative interviews following the CFIR framework to identify individual-, inner-, and outer-setting climate and implementation of evidence-based practices within each clinic
 - Administration of quantitative measures pre-, mid-, and post-intervention to further assess barriers and facilitators experienced by providers and PSSs in the integration and implementation of Horyzons
2. Evaluation of engagement of the platform and attrition of client participants across 12 months to assess acceptability of Horyzons as a routine clinical intervention within NC FEP clinics.
3. Evaluation of psychological outcomes (loneliness and social support) in addition to use of services (e.g., emergency department, hospitalization, outpatient services) to assess potential benefits (e.g., stability in symptoms) as a result of engagement with Horyzons.

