Study Rationale	The purpose of the present study is to investigate the barriers and facilitators to implementing a moderated online social media platform with therapeutic content, Horyzons, as a part of routine care received at first-episode psychosis (FEP) clinics across North Carolina.
Study Objective(s)	
Examine the implementation and integration Horyzons at NC FEP clinics as part of routine clinical care through the following objectives:
 
 1. Identifying the unique barriers and facilitators in implementing Horyzons at each FEP clinic as part of standard care and distinct implementation strategies 2. Evaluate client engagement with Horyzons and attrition as part of clinical care across 12 months 3. Assess change in clients' psychological measures across 12 months and use of emergency and social services across 12 months prior and during engagement with Horyzons platform
Test Article(s) (If Applicable)	Horyzons is a private digital platform that includes curated therapeutic content surrounding issues such as generalized anxiety, social anxiety, social functioning, depression, and distress tolerance. The site also includes a social media function, in which participants and peer support specialists (PSS) can post text, images, and videos. The site is moderated by graduate students and trained fs.
Study Design	This is an open trial enrolling both clients from NC FEP clinics and clinicians and PSSs. FEP clients will participate in the use of Horyzons, a novel digital intervention, which has previously demonstrated benefits to this population and complete psychological measures. FEP clinicians and PSSs will take part in qualitative interviews and surveys to identify unique barriers and enablers in integrating Horyzons as a clinical service within FEP clinics.
Client Participants	
Inclusion Criteria
 
Key Criteria for Inclusion and Exclusion:
 
 1. Clients must be between the ages of 16 and 35 2. Clients must have a diagnosis of schizophrenia, schizoaffective disorder, schizopreniform disorder, or Unspecified Schizophrenia Spectrum or Other Psychotic disorder 3. Clients must be receiving services at one of the five FEP clinics in North Carolina (OASIS, Encompass, Eagle, SHORE, or AEGIS) or one of their stepdown outpatient clinics (STEP and TIDES) 4. Clients must not have had thoughts of harming themselves in the month before enrollment

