Evaluation	
Primary outcomes – Identification of barriers and enablers to implementing Horyzons to assess each clinic's unique circumstances to integrate Horyzons as part of routine clinical care.
 
Secondary outcomes – Client engagement with the Horyzons platform and attrition in the study to assess Horyzons as part of routine clinical care.
 
Tertiary outcomes – The UCLA Loneliness Scale and MOS Social Support Survey (total score) will be used to assess subjective feelings of loneliness and social support. Further, clients' use of emergency and social services to further evaluate Horyzons benefit in clinical outcomes.

Safety Evaluations	A safety plan for Horyzons was developed before participants joined the Horyzons digital platform by [name] and study coordinator [name]. All safety measures were approved by the director of each NC FEP clinic.
Statistical and Analytic Plan	Analyses will primarily be thematic qualitative analysis in nature, along with quantitative measure of barriers and enablers. Semi-structured interviews will be coded to identify each clinic's unique situation to integrate Horyzons as part of a clinical offering within their FEP clinic. Secondary analyses will include an examination of client participation rates and utilization of the platform across sites and their attrition. We will also evaluate changes in mean loneliness and social support across 12 months.
Data and Safety Management	Privacy and online safety will be managed in accordance with the 'Online social networking' guidelines published by 'Cybersmart', a national cybersafety and cybersecurity education program managed by the Australian Communications and Media Authority (ACMA). Online safety will be monitored by Horyzons moderators (clinicians involved in the project, peer support specialists, graduate students in the Department of Psychology and Neuroscience) with supervision from the Principal Investigator, [name], or Licensed Clinical Psychologist and research collaborator, [name]. [name] will function as the Project Medical Officer.

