Young people receiving services from CSC programs typically attain significant positive outcomes including decreased rates of hospitalization and improved social and occupational functioning within an average of two years of treatment (2). However, treatment benefits are usually not maintained over time (3-4) in particular when clients are less engaged in treatment or have recently experienced discharge from the program. For instance, the benefits of early intervention seen at the end of 2 years may not persist at 5 years (5). There is a need, therefore, to explore ways to provide ongoing support for individuals experiencing first episode psychosis. This support should address especially what some have called "social network crisis" experienced by the FEP population. This refers to the limited social networks and community support that individuals with psychosis generally have. Innovative approaches through internet-based interventions may shed valuable light on the issue of maintaining treatment effects derived from FEP services and offer additional social support to those enrolled in such services.

Additionally, the proposed research is aligned with the NIMH strategic objective of striving for prevention and cures through the study of mechanisms of therapeutic action. Specifically, it aligns with the goals of developing new treatments based on discoveries in the behavioral sciences and testing interventions for effectiveness in community practice settings. This project in essence builds and extends the findings of research on the effectiveness of CSC and looks to determine whether these benefits can be extended beyond CSC in a web-based platform delivered to individuals in the community.

We suggest that internet-based interventions have the potential to provide cost-effective, non-stigmatizing, constantly available support to FEP people. These interventions, especially those aimed to strengthen social networks, can be used to counteract social isolation and disadvantage; increase functional outcomes and engagements (6); reduce symptomatology; and improve uptake and acquisition of therapeutic strategies. These also provide an entirely new approach in which participants can safely self-disclosure, take positive interpersonal risks, gain perspective, broaden and rehearse coping skills, obtain encouragement and validation, and learn how to solve problems (7).

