5.2 SECONDARY OUTCOME MEASURES

1. Mean Change in UCLA Loneliness Scale Score [Time Frame: Baseline, Post-treatment, up to 12 months]

The UCLA Loneliness scale is a 20-item scale. Answers are on a 4-point scale with options "I often feel this way," "I sometimes feel this way," "I rarely feel this way," and "I never feel this way." Possible scores range from 20 to 80. Higher scores reflect worse outcomes (greater feelings of loneliness). The UCLA Loneliness Scale is a part of the PhenX Toolkit.

1. Mean Change in Medical Outcomes Study (MOS) Social Support Survey - total score [Time Frame: Baseline, Post-treatment, up to 12 months]

The MOS Social Support Survey is a 19-item scale. Answers are on a 5-point scale with options "none of the time", "a little of the time", "some of the time", "most of the time", and "all of the time". Possible scores range from 19 to 95. Higher scores reflect higher feelings of social support (more perceived social support). The MOS Social Support Survey is a part of the PhenX Toolkit.

2. Quantitative Summaries of Participant Experience in Post-Treatment Feedback [Time Frame: up to 12 months]

This quantitative data will be collected post-treatment from clients and clinicians. Feedback forms will prompt participants to answer questions regarding their experience with the platform on a scale of 1 to 5, with higher scores reflecting a more positive experience. Frequency counts will be included here.

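### Section 3 and the synopsis word uncontrolled pre-post change as Horyzons benefit, and name symptom stability, which no listed outcome measures

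*Combined protocol and SAP*

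**What the plan says.** The synopsis describes the design: "This is an open trial enrolling both clients from NC FEP clinics and clinicians and PSSs". Every client receives the platform and no comparison group is described. The third study objective there is neutral: "Assess change in clients' psychological measures across 12 months and use of emergency and social services across 12 months prior and during engagement".

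Two other places go further. Section 3, item 3, says the loneliness, social support and service-use data serve "to assess potential benefits (e.g., stability in symptoms) as a result of engagement with Horyzons". The Evaluation part of the synopsis lists "clients' use of emergency and social services to further evaluate Horyzons benefit in clinical outcomes".

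The planned client analyses are in Sections 5.2 and 5.3. They are mean change on two scales (for example "Mean Change in UCLA Loneliness Scale Score"), feedback frequencies, platform engagement and attrition, and service use before and after starting Horyzons.

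On concurrent care, Section 2.2.1 states: "Clients must be receiving services at one of the five FEP clinics in North Carolina", or at a step-down clinic. It also requires recent psychiatric medication management and no psychiatric hospitalization in the preceding three months. Section 1 says of this kind of care: "Young people receiving services from CSC programs typically attain significant positive outcomes". It then adds that gains are usually not maintained over time, particularly with lower engagement or after recent discharge.

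**The concern.** Item 3 of Section 3 contains two claims that the study cannot deliver.

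The first is causal. Crediting change to engagement requires some estimate of what would have happened without it. The plan has no control group, no historical comparator and no analysis linking amount of use to outcome.

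The second concerns symptoms. The only example of benefit that Section 3 gives is a symptom outcome, yet no symptom outcome is defined.

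At stake is what the final report may say. Section 5.4 says the study will inform future implementation of Horyzons in North Carolina. An author who followed Section 3 literally could report an effect of Horyzons, or a statement about symptoms, that the data do not carry. The same author could also conclude wrongly that Horyzons failed.

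**Working it through.** The plan states no effect size, SD, test or power (Section 5.4), so it has no figure to reproduce. The check is a comparison of passages plus two illustrations on stated assumptions.

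**1. Attribution.** Sections 5.2 and 5.3 specify change within the single group. Section 2.1 provides Horyzons as part of routine clinical care, so the platform and that care are not separated by design. No analysis in Section 5 relates logins, activities or posts to loneliness, support or service use.

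**2. Symptoms.** The client instruments are:
- baseline (4.1.2): demographics and history, UCLA Loneliness, MOS Social Support;
- 6 and 12 months (2.1, 4.2.1, 4.2.2): the same two scales plus a feedback survey.

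No symptom scale appears at any visit or in Sections 5.1 to 5.3. Section 6.1 mentions monitoring of psychotic symptoms within the platform, but as a clinical safety procedure. Service use is at most an indirect proxy.

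**3. Hospitalization comparison.** Inputs: 12 months before and 12 months during use (synopsis, Objective 3), and no psychiatric admission in the last 3 months before enrollment (2.2.1). Assumptions: each client's admission rate is constant within each period, the pre-window ends at enrollment, and follow-up is complete.

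At-risk months before entry: 12 − 3 = 9. At-risk months after entry: 12.

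Expected post/pre ratio = 12 × (1 − f) / 9, where f is the proportional fall in the rate from any cause.

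| f | Ratio |
|---|---|
| 0 | 12/9 = 1.33 |
| 0.10 | 10.8/9 = 1.20 |
| 0.25 | 9/9 = 1.00 |
| 0.40 | 7.2/9 = 0.80 |

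The rate itself cancels. At 0.03 admissions per month (assumed), 0.27 are expected before entry and 0.36 after, again a ratio of 1.33. With no change in rate the comparison shows an apparent rise. If clinic care alone cut the rate by 40%, it would show an apparent 20% fall with no Horyzons effect. The direction depends on a background trend that the documents do not quantify.

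**4. Scale scores.** Illustration only, since the plan names no test. Assume a two-sided 5% paired t test, no Horyzons effect, and background drift of d SDs of the change score. The chance of a significant result in the direction of the drift is the upper tail of a noncentral t with n − 1 degrees of freedom and noncentrality d√n, beyond the 97.5% point of t.

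| d | n = 50 (Section 2.2) | n = 40 (Section 8) |
|---|---|---|
| 0 | 2.5% | 2.5% |
| 0.1 | 10% | 9% |
| 0.2 | 28% | 23% |
| 0.3 | 55% | 46% |

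By symmetry, the same figures apply to apparent worsening if the drift is downward.

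**The case against.** The best defence is that the plan is already mostly descriptive. Objective 3 in the synopsis speaks only of change, and so do Sections 5.2 and 5.3. Section 3 says potential benefits and refers to an early stage of treatment development, and Section 5.4 calls the study exploratory. The only stated hypotheses (Section 3.1) concern barriers and facilitators. In the synopsis, the benefit phrase attaches to service use and not clearly to the two scales. All of this stands. It limits the point to two sentences, but it does not make those sentences supportable.

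A reader might infer three stronger things, none of which the documents support:

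- **That any improvement would be reported as a Horyzons effect.** No Section 5 analysis makes that attribution, and the hospitalization window at a constant rate works against Horyzons.
- **That clients are on a steadily improving course under usual care.** Section 1 also says gains usually fade, step-down clients are eligible, and nothing requires clinic care for the full 12 months. The outcomes it names are hospitalization and social and occupational functioning, not loneliness or perceived support.
- **That regression to the mean would produce improvement in loneliness.** No entry criterion selects lonely or poorly supported clients. Sections 2.2.1 and 4.1.1 select for clinical stability, so no size or favourable direction can be assigned to such an effect.

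**Conclusion.** The point holds as a mismatch between wording and design. Item 3 of Section 3, and the service-use sentence in the synopsis, promise an assessment of Horyzons benefit that an uncontrolled pre-post comparison cannot give. The symptom example has no outcome behind it. Both follow from the text alone and need no assumption.

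The size of any bias is unknown, and so is its direction. The one component that follows from the plan's own rules is the hospitalization ratio of 1.33 under no effect, which assumes constant rates and complete 12-month windows. It applies to psychiatric admissions and not directly to other service use. The drift figures for the scales rest wholly on assumed drift and an assumed test.

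Severity is minor to moderate. The synopsis and Section 5 rank these outcomes differently, but neither makes them primary, and descriptive reporting of change remains legitimate.

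**What to change.** - In Section 3, item 3, delete the symptom example in brackets and the closing phrase that credits benefit to engagement. Say instead that the data will describe change in loneliness, social support and service use over 12 months of Horyzons access alongside clinic care.
- In the Evaluation part of the synopsis, replace the benefit wording for service use with the before-and-during description already used in Objective 3. Objective 3 itself needs no change.
- In Sections 5.2 and 5.3, state that change will be reported with 95% intervals and will not be attributed to Horyzons.
- Beside the hospitalization result, note that the last three pre-enrollment months are admission-free by the entry rule.

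The cost is wording and interval estimates. No new data, visits or participants are needed. The downside is a more modest claim.

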3.1 OUTCOMES

Based on previous interviews with providers and peer support specialists, we hypothesize providers and/or PSS will report barriers that may be unique to each clinic as each experiences different outer-, inner, and individual-setting circumstances. Previous barriers, which will likely be reiterated and further described include time constraints, workload, staffing turnover, and perception of the implementation of a new intervention within care. Facilitators are also likely to be distinctive to each clinic, including the support of the team lead in the implementation of Horyzons and time dedicated to Horyzons within care, perception and desire to incorporate evidence-based interventions into clinical treatment to improve client outcomes, and goals and aims of Horyzons aligning with their role.

4 STUDY PROCEDURES

4.1 SCREENING & BASELINE PROCEDURES

4.1.1 SCREENING PROCEDURES

For recruitment of client participants, the research study coordinator will communicate with providers and other members of the treatment team to explain the project and discuss eligibility criteria for the study. If agreed to by the clinical team at each site, the research team will review the clinical census at each clinic and/or identify potential participants (clients) via the EPIC system. Clinical team members will be asked to review their current caseloads to identify potentially eligible participants (i.e., patients who are currently receiving services at OASIS, SHORE, Encompass, Eagle, AEGIS, STEP and TIDES and are considered clinically stable without current active suicidal ideation). The study coordinator and research assistant will engage in discussion with the treatment team to help identify appropriate clients for inclusion in the project. When participants have been identified and expressed interest in participation to their clinician or other treatment provider, the research study coordinator or RA will reach out to the client in their preferred method of contact (i.e., in person at the clinic or via phone/email) to discuss the project and complete an initial screen to confirm the inclusion and exclusion criteria.

If clients self-refer (in response to flyers and/or website form), the research coordinator and PI will consult with their treatment team first before screening the client (i.e., to make sure there are no issues that prevent them from safely participating in the study).

Clinicians will be consulted prior to each contact with a prospective participant and asked to advise the research team if any prospective participant should not be contacted.

For provider and PSS participation, research staff will reach out to the five FEP clinics (OASIS, SHORE, Encompass, Eagle, and AEGIS) through the program directors. Due to the long-standing relationship and close working partnership of the PI with programs, research staff are connected to program directors. After an explanation of the study is given to the program directors, program directors will be asked to discuss the study with their team prior to research staff reaching out to each team member individually. Providers and/or PSS will then be contacted by research staff to determine if they would like to participate and be screened to determine eligibility.

4.1.2 BASELINE PROCEDURES

The study coordinator will meet virtually with client participants for approximately 45 minutes to complete all baseline measures. Informed consent and HIPAA authorization will be completed first via DocuSign's electronic consent platform, followed by a demographic and characteristic form collecting basic information about sex, age, ancestry, education (including parent education levels and zip code), cigarette/alcohol use, and basic history of medication/psychosis (including DUP). This will be followed by two psychological measures: the UCLA Loneliness Scale and MOS Social Supports Survey. Once the baseline study measures are complete, the study coordinator will guide clients through a 10-minute orientation to the Horyzons platform, including creating their personal profile and learning the features of the site. Client participants will be paid \$20.00 via Visa gift card for their time and completion of the visit.

The study coordinator will verbally highlight over the phone the study aims, what will be asked of the provider, the timeline of their participation, and that their participation is voluntary for each provider participant at the end of the screening. The provider participants will then be sent the consent forms via DocuSign to sign. In the email and at the top of the consent form in DocuSign there will be a number to call if they have questions. The language will explicitly indicate to call the number prior to consenting and signing the document if they have questions. The provider participants will then be sent the baseline surveys (demographics and CPCRN FQHC Survey) to complete on their own. Providers and PSS will be compensated \$30 for completing the consent and baseline measures.

